### **Importance of the Knowledge To Be Gained**

Currently, finding a suitable peripheral vein for access continues to be a frequent challenge for healthcare providers and a significant burden to the patient; issues that are hoped to be addressed by the study device. Due to the sheer volume of peripheral venous catheter placements within the in-hospital setting and the associated detriments to the patient when repeated attempts are needed, any improvement in reducing the number of attempts of peripheral vein cannulations, prolonging the patency of these catheters, and reducing catheter associated complications can have a significant impact on overall patient care throughout the entire in-hospital patient population.

The proposed clinical trial will establish the potential of incorporating a novel NIR vein finder into clinical practice to improve peripheral venous access for in-hospital patients who are considered a 'difficult stick'. Incorporation of such devices, if found to be successful, can fundamentally change patients' experience and reduce complication rates.

## **Limitations**

Overall it is felt that the study has a very robust design. Yet, limitations include bias by any Vascular Access Team member who may favor one method and therefore might create more favorable results with the method of subjective preference (observer-expectancy effect and experimenter bias).

The follow-up was felt to be adequate since most complications are expected to present during the hospital stay. However, long-term complications, such as thrombophlebitis, might be slightly underestimated due to its sometimes later presentation even after removal of the catheter or in patients who have been transferred to a different facility with the catheter still in place. Nevertheless, there is currently no reason to believe that long-term outcomes of a successful peripheral venous catheter are dependent on the method of catheter placement and therefore it is not expected that the study results will significantly be affected.

NIR vein imaging might require a learning curve. To minimize the issue, all Vascular Access Team members have been trained with the device and had to use the device independently during routine patient care for at least 20 cases before being able to participate in the study.

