### **Follow-Up (for in-patients only)**

A member of the Vascular Access Team will see the patient in person three days after peripheral venous cannulation and each day thereafter according to routine practice. At the follow-up evaluation patency of the peripheral venous catheter and any complications associated with the peripheral venous catheter will be clinically assessed and documented. Follow-up will be completed once the patient has been discharged from the hospital or once the peripheral venous catheter placed as part of the study has been removed or replaced.

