## **Study Monitoring and Safety Plan**

### **Study Monitoring**

After the first patient has been enrolled, the principle investigator will review the collected data every four weeks with other members of the study staff. At each research meeting, the principle investigator will evaluate study progress and assess protocol compliance. This will include the informed consent procedure, compliance with eligibility criteria, and identification of protocol violations. The principle investigator will also review all collected data to verify data accuracy, consistency, and integrity. The patients will be physically evaluated 3 days after the procedure by a Vascular Access Team member according to routine practice, unless discharged home or otherwise not available in-hospital, to assess for procedure related adverse events. The principle investigator will review any reports that could be pertinent to a potential adverse event. The principle investigator will be responsible for reviewing data from any adverse event and determining, if applicable, whether the research should be altered or stopped. Any decision to alter or stop enrollment will be reported to the IRB.

Any untoward medical event considered related or possibly related to study participation will be considered an adverse event. Serious adverse events (SAE) will be defined as stated in the IRB SAE reporting policy. Adverse events will be graded for severity according to NCI-CTCAE (version 4.0). For the purpose of safety reporting, the study period will be considered from the day of the procedure to the day of the last follow-up. All adverse events of grade II or greater attributable to study participation will be reported to the IRB. Multiple occurrences of an adverse event that, based on an aggregate analysis, is determined to be an unanticipated problem independent of the severity grade will be reported to the IRB. Any SAEs related to study participation will be reported within 5 business days of the PI learning of the event.

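### Follow-up is justified by the hospital stay but ends at catheter removal, so complications first appearing between removal and discharge are not captured

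*Combined protocol and SAP*

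**What the plan says.** All references are to the combined protocol and SAP.

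- **Limitations** gives the reason for the follow-up length: "The follow-up was felt to be adequate since most complications are expected to present during the hospital stay".
- **Follow-Up (for in-patients only)** has a team member see the patient "three days after peripheral venous cannulation and each day thereafter according to routine practice". It closes follow-up at discharge or "once the peripheral venous catheter placed as part of the study has been removed or replaced".
- **Study Monitoring** defines the safety window by reference to that rule: "the study period will be considered from the day of the procedure to the day of the last follow-up". It also provides a physical evaluation on day 3 for patients still available in hospital, without saying whether the catheter must still be in place.
- **Limitations** then concedes that "long-term complications, such as thrombophlebitis, might be slightly underestimated", and gives as one reason "due to its sometimes later presentation even after removal of the catheter". It sets this aside because it sees no reason for the long-term outcome of a successful catheter to depend on the placement method.
- **Data Collection** lists hematoma, phlebitis, thrombophlebitis, infiltration and nerve damage as follow-up outcomes. **Secondary Objectives** makes complication rates and catheter durability objects of comparison.

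**The concern.** The argument for adequacy rests on one window, the hospital stay. The rule delivers another: time with the study catheter in place, or time to discharge if that is shorter. The two differ for every in-patient whose catheter comes out before discharge. In that interval the patient is still on the ward and easy to observe, yet is outside both complication follow-up and safety reporting. The complication that the plan names as liable to appear late is one that can fall there.

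Two things are at stake. Complication rates, a secondary and safety outcome, may be understated by an amount that the plan calls slight without a figure. The observation window is also set by catheter durability, which may differ by arm. If it does, the arms are watched for different lengths of time, and the plan's unspecified routine tests (Data Analysis and Statistical Methods) make no provision for that.

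**Working it through.** **1. The plan's own figure.** No figure in the documents bears on this point. The only calculation is the sample size for the primary endpoint, checked here to see whether it is touched. Inputs from Sample Size and Power Determination: 50% against 70% success, two-sided alpha 0.0167, 80% power. With pooled variance under the null and no continuity correction,

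n = [z(1−α/2)·√(2·0.6·0.4) + z(0.80)·√(0.5·0.5 + 0.7·0.3)]² / 0.2² = 125 per group after rounding up, with power 80.3% at n = 125.

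This matches the plan. Primary success is recorded at cannulation, so the end of follow-up does not affect it.

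**2. The windows side by side.**

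| Source | Window ends at |
|---|---|
| Limitations (reason given) | End of hospital stay |
| Follow-Up | Discharge, or catheter removal or replacement, whichever is first |
| Study Monitoring (safety period) | Day of last follow-up, so the same as the row above |
| Study Monitoring (day-3 evaluation) | Day 3 if still available in hospital; catheter status not mentioned |

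Take an in-patient whose catheter is removed on day 4 and who develops thrombophlebitis at the site on day 6, still in hospital. Follow-up and the safety period both ended on day 4, and the day-3 evaluation came before the event. The event is not captured. If removal had been on day 2 and the event visible on day 3, the day-3 evaluation might have found it, but the Follow-Up section would already have closed that patient's follow-up. The two sections do not say which governs.

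**3. Size of the loss, on assumed values only.** The documents give no complication rate, dwell time, length of stay or share of late events. Take 400/3 ≈ 133 per arm and treat all as followed in-patients, which is generous because outpatients have no follow-up. Let p be the true rate to discharge and m the share of events first appearing after removal. The recorded rate is p(1 − m).

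| Assumed p | Assumed m | Recorded rate | Events per arm: true → recorded |
|---|---|---|---|
| 10% | 10% | 9.0% | 13.3 → 12.0 |
| 10% | 25% | 7.5% | 13.3 → 10.0 |
| 10% | 50% | 5.0% | 13.3 → 6.7 |

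Over p from 5% to 15% and m from 10% to 50%, the recorded rate runs from 0.05 × 0.50 = 2.5% to 0.15 × 0.90 = 13.5%. Whether the loss is slight depends on m, which the plan does not state.

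**4. Comparison between arms.** If m is the same in every arm, the ratio of rates is unchanged, because p₁(1−m)/[p₂(1−m)] = p₁/p₂; only absolute rates and differences shrink. If dwell differs, the result depends on when the risk arises. Suppose, purely for illustration, mean dwell of 3 and 4 days, a small equal daily risk h, and a stay of L days longer than both.

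- *Risk continues unchanged after removal.* The current rule records about 3h and 4h, a ratio of 4/3, or 33% more in the longer-lasting arm. Following to discharge gives Lh in both arms, a ratio of 1. The excess was an artefact of observation time.
- *Risk exists only while the catheter is in place.* The true counts are about 3h and 4h. Following to discharge leaves the ratio at 4/3. A rate per catheter-day is h in both arms, a ratio of 1.

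The same 33% is artefact in one case and real in the other. The documents do not say which applies, so the direction and size of any bias cannot be derived from them.

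**The case against.** The strongest reply is that the plan already discloses the weakness. Limitations says only that most complications are expected in hospital, and then states that events after removal may be underestimated. That stands against any reading that the plan hides the problem. It does not meet the narrower point: the plan treats this as a long-term matter and does not say that its own stopping rule creates the gap in patients still in hospital.

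Four stronger readings are tempting, and the documents do not support them.

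- *That thrombophlebitis is simply missed.* Events while the catheter is in place are captured, the day-3 evaluation may catch some early removals, and the principal investigator reviews reports pertinent to possible adverse events. These narrow the gap without closing it.
- *That the no-dependence statement contradicts the objectives.* Expecting no late difference is compatible with planning to compare complications. There is tension with the hypothesis of longer-lasting catheters in Study Objectives, because the statement assumes part of what is to be compared, but there is no logical contradiction.
- *That the rule penalises the better method, by 33% or any other amount.* As shown above, this holds only if risk persists after removal and dwell differs by arm. Neither is established.
- *That a particular share of events, such as 20–40%, is lost.* No source in the documents gives one.

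It is also fair that the follow-up tracks routine practice and that only secondary and safety outcomes in in-patients are involved. This limits the importance of the point but does not make the stated reason match the rule.

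**Conclusion.** The point holds in a limited form. The reason given for adequate follow-up refers to the hospital stay, while the rule stops complication follow-up and safety reporting at catheter removal or replacement if that comes first. Listed complications first appearing between removal and discharge are lost by rule, apart from what one day-3 evaluation may find. The length of observation also depends on durability, a compared outcome.

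The primary endpoint, the 125 per group and the 80% power are unaffected. The size of the loss and the direction of any between-arm bias are unknown; the figures of 12.0 to 6.7 recorded out of 13.3 events rest wholly on an assumed 10% rate and assumed late shares of 10% to 50%. This is an inexpensive improvement worth making, not a flaw that threatens the trial's main conclusion.

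**What to change.** 1. In Follow-Up and Study Monitoring, extend complication ascertainment and the safety-reporting period to hospital discharge for all in-patients. After the study catheter is out, use one chart check at discharge for the complications listed in Data Collection at the study site, with no added visits.
2. In Data Collection and Risks, keep identifiers until that check is done. Both sections now provide for their removal once follow-up is complete, which could make the check impossible.
3. Record whether each event was found at the bedside or by chart.
4. In Data Analysis and Statistical Methods, report complications by arm both per patient to discharge and per catheter-day, since each answers a different question when dwell differs.
5. Reconcile the day-3 evaluation in Study Monitoring with the stopping rule in Follow-Up.
6. In Limitations, restrict the statement that late outcomes do not depend on method to the period after discharge.

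The cost is protocol wording, one chart review per in-patient and identifiers held somewhat longer. Ascertainment would be at the bedside before removal and by chart after it, so detection may be less sensitive in the later interval; item 3 makes that visible. Recorded complication rates may look slightly higher. Events after discharge or transfer remain outside the window and should stay listed as a limitation.

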## **Study Resources and Finances**

### **Institutional Resources**

The study utilizes several existing resources available at Lahey Hospital & Medical Center. This does include the completed purchase of two VeinViewer devices which are already in clinical use at the institution.

The Vascular Access Team at Lahey Hospital & Medical Center performs approximately 10 peripheral venous access placements in the inpatient setting per day during regular business hours. The Vascular Access Team leader and members of the Vascular Access Team are investigators or collaborators of the study. The study is supported by the Department of Surgery at Lahey Hospital & Medical Center.

Support for statistical questions will be obtained through an established collaboration with the Clinical and Translational Science Institute at Tufts University.

### **Financial Resources**

The study is supported through the institutional infrastructure. The cost of statistical analysis will be covered through departmental funds.

### **Conflict of Interest**

Any investigator who has a conflict of interest with this study (patent ownership, royalties, or financial gain greater than the minimum allowable by Lahey Health Corporate Compliance, etc.) cannot participate in this study. All investigators will follow the applicable Lahey Health conflict of interest policies.

